18.0 Data Management and Analysis

18.1 Describe the data analysis plan, including any statistical procedures. This section applies to both quantitative and qualitative analysis.

Response: The project serves as a pilot to demonstrate our ability to administer high intensity interval training in older individuals and provide preliminary data to aid power calculations in future studies. With this in mind we will compare baseline and endpoint parameters using a paired student's T-test for the following parameters: SPPB scores, ADLs, Q-LES-Q-SF, quadriceps strength, and VO₂MAX, and in our ELISA analysis of the inflammatory biomarkers and LC-MS measurement of serum free and total testosterone. For microRNA analysis we will examine differentially expressed miRNA using statistical analysis that includes adjustment for false positives.

18.2 If applicable, provide a power analysis.

NOTE: This may not apply to certain types of studies, including chart/records reviews, survey studies, or observational studies. This question is asked to elicit whether the investigator has an adequate sample size to achieve the study objectives and justify a conclusion.

Response: This is a pilot feasibility study. No power calculation is deemed necessary.

18.3 Describe any procedures that will be used for quality control of collected data.

Response: Data is subjected to quality review by research staff at time of data entry. The data is cleaned up using a logic check system to ensure accuracy. Data that does not pass logic check criteria are queried for clarification.

19.0 Confidentiality

A. Confidentiality of Study Data

Describe the local procedures for maintenance of confidentiality of study data and any records that will be reviewed for data collection.

19.1 A. Where and how will all data and records be stored? Include information about: password protection, encryption, physical controls, authorization of access, and separation of identifiers and data, as applicable. Include physical (e.g. paper) and electronic files.

Response: Data in this study refers to clinical data (via patient surveys, questionnaires, and assessments), lab generated research data such as ELISA analysis of inflammatory biomarkers, serum free and total testosterone levels, and sequenced data of miRNA from serum.

A unique subject number will be assigned to each subject at inclusion, immediately after informed consent has been obtained. This number will serve as the subject's identifier in the trial as well as in the storage database. Only the PI or designated research personnel will be able to link the subject's data to the identified subject via an identification list that will be stored on a secured research SharePoint that is accessible only to designated and approved research personnel.

Obtained health data, documents, and research generated data will be stored in a passkey protected cabinet in the Co-PI's laboratory located at CTRC 8031, the laboratory requires ID and clearance. The data will not contain any identifiers. The PI will store that file in the passkey protected cabinet.

Clinical and research data collected will be stored digitally on PI and Co-PI's computers. To ensure security of data, using the assigned letter code as the new identifier, no medical record or any identifier will be placed in that file. Additionally, all computers are located in locked rooms and are password protected.

The Center for Excellence in bioinformatics and laboratory sciences will receive de-identified samples for sequencing. Only the PI will be able to identify samples and will work closely with biostatisticians to ensure anonymity of samples is maintained during the statistical analyses.

19.2 A. How long will the data be stored?

Response: Indefinitely

19.3 A. Who will have access to the data?

Response: The PI, Co-PI and delegated research staff (research assistants listed in this protocol) will have access to data as necessary for data entry, data clarification and analysis. De-identified specimens will be processed by lab staff (listed in this protocol)

The consent will include language asking participants if they are ok with the research data being used for other relevant research beyond the scope of this study. In addition, the consent document will request permission to contact participants for additional follow-up analyses if deemed appropriate.

19.4 A. Who is responsible for receipt or transmission of the data?

Response: The Principal Investigator and delegated research staff will be responsible for the transmission of the data.

19.5 A. How will the data be transported?

Response: Data generated in the PI's lab will be entered in the data file. These data are de-identified and transferred to co-investigators for further analysis as needed.

Physical data will be transported from the site of generation at the VAMC to storage sites at the CTRC by the PI and other members of the study team.

De-identified miRNA sequence data will be accessed remotely using the core facility system with a provided log in and password info.

B. Confidentiality of Study Specimens

Describe the local procedures for maintenance of confidentiality of study specimens.

N/A: No specimens will be collected or analyzed in this research.
(*Skip to Section 19.0*)

19.6 B. Where and how will all specimens be stored? Include information about: physical controls, authorization of access, and labeling of specimens, as applicable.

Response: All samples will be labeled using the same code mentioned above to de-identify the samples.

All samples will be stored in -80C freezer in the Research Core lab, Room 105, in the Research Building 20 of the VA Hospital. The lab is secure and cannot be accessed without ID badge and the proper authorization.

19.7 B. How long will the specimens be stored?

Response: Indefinitely

19.8 B. Who will have access to the specimens?

Response: The specimens will be accessed by the lab staff member listed in this IRB.

In future, these de-identified samples could be made available to other researchers and partners (new projects utilizing these samples and associated data will go through IRB approval)

19.9 B. Who is responsible for receipt or transmission of the specimens?

Response: The PI's lab staff listed in this IRB will be responsible for receiving, handling, storage and further distribution of samples.

19.10 B. How will the specimens be transported?

Response: De-identified specimens will be transferred from the point of collection to the PI's research lab in building 20 of the VA Western New York. Additionally, processed miRNA samples will be transported to the New York State Center of Excellence Bioinformatics & Life Sciences.

20.0 Provisions to Monitor the Data to Ensure the Safety of Subjects

N/A: This study is not enrolling subjects, or is limited to records review procedures only. This section does not apply.

NOTE: Minimal risk studies may be required to monitor subject safety if the research procedures include procedures that present unique risks to subjects that require monitoring. Some examples include: exercising to exertion, or instruments that elicit

suicidality or substance abuse behavior. In such cases, N/A is not an acceptable response.

20.1 Describe the plan to periodically evaluate the data collected regarding both harms and benefits to determine whether subjects remain safe.

Response: During baseline, endpoint, and follow-up assessments a physician will be present to identify acute markers that would indicate a risk to safety. During the exercise phase of our experiment, we will evaluate heart rate and blood pressure data to ensure both are within acceptable limits. Additionally, participant self reported concerns will be addressed as soon as possible.

20.2 Describe what data are reviewed, including safety data, untoward events, and efficacy data.

Response: To assess safety we will examine blood pressure and heart rate in addition to participant self reports of health status.

20.3 Describe any safety endpoints.

Response:

- Significant drop in systolic blood pressure (20 mmHg) or a failure of systolic blood pressure to increase with increasing intensity
- Excessive rise in blood pressure (systolic > 220 mmHg or diastolic > 105 mmHg)
- Drop in diastolic blood pressure ≥ 15 mmHg
- Failure of heart rate to increase with increasing intensity
- Participant self reports of
 - *Injury*
 - lightheadedness, confusion, ataxia, dizziness, nausea
 - Severe subject fatigue

20.4 Describe how the safety information will be collected (e.g., with case report forms, at study visits, by telephone calls with participants).

Response: Body weight and heart rate will be collected during participant visits, including participant self reports.

20.5 Describe the frequency of safety data collection.

Response: Safety data will be collected during baseline and endpoint assessments and at each of the thrice weekly exercise sessions.

20.6 Describe who will review the safety data.

Response: Safety data will be reviewed by the research team (Drs. [name], [name], [name], and [name]).

20.7 Describe the frequency or periodicity of review of cumulative safety data.

Response: Cumulative safety data will be reviewed weekly, unless notification of a significant event needing immediate attention.

20.8 Describe the statistical tests for analyzing the safety data to determine whether harm is occurring.

Response: Risk of harm will be determined by safety data reaching or surpassing specific thresholds.

20.9 Describe any conditions that trigger an immediate suspension of the research.

Response: Suspension of the research for specific participants will be considered if safety parameters reach or surpass specific thresholds.

21.0 Withdrawal of Subjects

N/A: This study is not enrolling subjects. This section does not apply.

21.1 Describe anticipated circumstances under which subjects may be withdrawn from the research without their consent.

Response: Participants may be withdrawn if during safety evaluation they reach or surpass our specific thresholds for safety. Additionally, participants may be removed if they develop an injury that prevents further participation.

21.2 Describe any procedures for orderly termination.

NOTE: Examples may include return of study drug, exit interview with clinician. Include whether additional follow up is recommended for safety reasons for physical or emotional health.

Response: The clinical data and blood samples will be removed as per patient request.

21.3 Describe procedures that will be followed when subjects withdraw from the research, including retention of already collected data, and partial withdrawal from procedures with continued data collection, as applicable.

Response: In the event that the samples degrade, and the subject is not included in the study, the collected samples will be destroyed as per EHS guidelines for managing biohazardous waste.

If the subject wishes to withdraw from the study, the subject's sample will be destroyed. No further data will be collected from this subject.

22.0 Risks to Subjects

22.1 List the reasonably foreseeable risks, discomforts, hazards, or inconveniences to the subjects related to their participation in the research. Consider physical, psychological, social, legal, and economic risks. Include a description of the probability, magnitude, duration, and reversibility of the risks.

NOTE: Breach of confidentiality is always a risk for identifiable subject data.

Response: The methodology is relatively low risk to participants, with the highest risk methods being blood draw, a maximal respiration test, and 36 exercise sessions (plus 1-2 optional sessions) over a 12 week period. Additionally, participants will be asked to travel to the Buffalo VAMC for assessments and exercise sessions, which thus includes the risk of transit. The overall probability of adverse events is low and in all but the most rare events, harm will be reversible.

22.2 Describe procedures performed to lessen the probability or magnitude of risks, including procedures being performed to monitor subjects for safety.

Response: We will perform safety monitoring of participants as necessary to minimize risk of harm.

22.3 If applicable, indicate which procedures may have risks to the subjects that are currently unforeseeable.

Response: Exercise testing and training carries inherent risks that may vary from participant to participant.

22.4 If applicable, indicate which research procedures may have risks to an embryo or fetus should the subject be or become pregnant.

Response: Not applicable.

22.5 If applicable, describe risks to others who are not subjects.

Response: Not applicable.

23.0 Potential Benefits to Subjects

23.1 Describe the potential benefits that individual subjects may experience by taking part in the research. Include the probability, magnitude, and duration of the potential benefits. Indicate if there is no direct benefit.

NOTE: Compensation cannot be stated as a benefit.

Response: This research has the potential to improve functional capacity and quality of life in study participants. This study also introduces participants to a maintainable exercise strategy for older individuals, who previously may not have considered exercise to be a viable option to maintain functional capacity.

24.0 Compensation for Research-Related Injury

N/A: The research procedures for this study do not present risk of research related injury (e.g. survey studies, records review studies). This section does not apply.

24.1 If the research procedures carry a risk of research related injury, describe the available compensation to subjects in the event that such injury should occur.

Response: There is no compensation for research related injury.

24.2 *Provide a copy of contract language, if any, relevant to compensation for research related injury.*

*NOTE: If the contract is not yet approved at the time of this submission, submit the current version here. If the contract is later approved with **different language regarding research related injury**, you must modify your response here and submit an amendment to the IRB for review and approval.*

Response:

25.0 Economic Burden to Subjects

25.1 *Describe any costs that subjects may be responsible for because of participation in the research.*

NOTE: Some examples include transportation or parking.

Response: Participants will be responsible for travel arrangements to the Buffalo VAMC training facility.

26.0 Compensation for Participation

25.1 *Describe the amount and timing of any compensation to subjects, including monetary, course credit, or gift card compensation.*

Response: Participants will receive remuneration in the form of a check of \$100 for completion of baseline assessments and \$300 for completion of endpoint assessments. This compensation is for time spent, travel expenses and participation in the study.

For participants allowing follow-up examination after the training program, we will provide a Fitbit activity monitor as well as a check for \$2500 for time spent, travel costs, and participation.

- N/A:** This study is not enrolling subjects, or is limited to records review procedures only. This section does not apply.
- N/A:** There is no compensation for participation. This section does not apply.

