6.0 Local Number of Subjects

6.1 *Indicate the total number of subjects that will be enrolled or records that will be reviewed locally.*

Response: *The initial plan to enroll 45 participants was disrupted due to the onset of the pandemic at which time patient recruitment/enrollment had ended. At this time no further recruitment of new participants will occur and we will only be completing the 27 subjects with their final visit. We will update the protocol and ICF to reflect this information.*

6.2 *If applicable, indicate how many subjects you expect to screen to reach your target sample (i.e. your screen failure rate).*

Response: We expect our screening success rate will be 20%, thus we will need to screen approximately 50 participants to reach our enrollment goals.

6.3 *Justify the feasibility of recruiting the proposed number of eligible subjects within the anticipated recruitment period. For example, how many potential subjects do you have access to? What percentage of those potential subjects do you need to recruit?*

Response: Data from the VA Western New York primary care facility indicates there were nearly 7,000 unique patient visits last year of individuals within our desired age range. From this pool we would need to recruit roughly 2 individuals

per month during the study period. Although we anticipate we will be successful in accomplishing this recruitment rate, the goal of this proposal is to determine the feasibility of doing so.

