8.0 Vulnerable Populations

If the research involves special populations that are considered vulnerable, describe the safeguards included to protect their rights and welfare.

NOTE: You should refer to the appropriate checklists, referenced below, to ensure you have provided adequate detail regarding safeguards and protections. You do not, however, need to provide these checklists to the IRB.

8.1 *For research that involves **pregnant women**, safeguards include:*

NOTE CHECKLIST: Pregnant Women (HRP-412)

Response: **N/A:** This research does not involve pregnant women.

8.2 *For research that involves **neonates of uncertain viability or non-viable neonates**, safeguards include:*

NOTE CHECKLISTS: Non-Viable Neonates (HRP-413), or Neonates of Uncertain Viability (HRP-414)

Response: **N/A:** This research does not involve non-viable neonates or neonates of uncertain viability.

8.3 *For research that involves **prisoners**, safeguards include:*

NOTE CHECKLIST: Prisoners (HRP-415)

Response: **N/A:** This research does not involve prisoners.

8.4 *For research that involves **persons who have not attained the legal age for consent to treatments or procedures involved in the research (“children”)**, safeguards include:*

NOTE CHECKLIST: Children (HRP-416)

Response: **N/A:** This research does not involve persons who have not attained the legal age for consent to treatments or procedures (“children”).

8.5 *For research that involves **cognitively impaired adults**, safeguards include:*

NOTE CHECKLIST: Cognitively Impaired Adults (HRP-417)

Response: **N/A:** This research does not involve cognitively impaired adults.

8.6 *Consider if other specifically targeted populations such as students, employees of a specific firm, or educationally or economically disadvantaged persons are vulnerable. Provide information regarding their safeguards and protections, including safeguards to eliminate coercion or undue influence.*

Response: The possibility exists that economically disadvantaged individuals may be included in our study, although this group is not specifically targeted.

Participants will be receiving remuneration for their effort, however, the amount chosen (~\$400) is fair based on the length of the study and that travel to the VAMC during the 3-4-month period is required.

For the post-HIIT examination, participants will be provided with a Fitbit activity monitor and \$250 dollars for their participation.

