Regional Tissue Oxygen Saturation: fNIRS will be used to measure blood flow to each subject's exercising quadriceps muscle during the maximal exercise test. The fNIRS device will be strapped atop the right quadriceps muscle using a neoprene sleeve prior to the VO₂max test and will remain in place through cessation of exercise and recovery. The fNIRS device communicates wirelessly via Bluetooth to a laptop computer for data acquisition. The fNIRS device is both small (~5 cm x ~7 cm x ~2.5 cm) and non-invasive.

Functional capacity and quality of life surveys: To assess functional capacity we will also administer an activities of daily living survey (ADLs - survey instrument attached), the quality of life, enjoyment, and satisfaction survey (Q-LES-Q-SF, instrument attached), and the physical activity enjoyment scale (PACES, instrument attached) to assess perceived enjoyment of the exercise protocol. In addition, the Pittsburgh Sleep Quality Index (PSQI – instrument attached) will be administered. For a duration of 7-days, leisure-time physical activity will be measured using Fitbit activity monitors.

Mental status: To assess mental status we will administer the VA-ST. Louis university Mental Status (SLUMS) examination (instrument attached) as well as the Cognivue Clarity.

Serum Collection: When participants return for the post-HIIT visit, we will also collect 80 mL as a follow-up to the previous analysis as well as to be used in blood cell metabolism experiments.

11.2 Describe what data will be collected.

NOTE: For studies with multiple data collection points or long-term follow up, consider the addition of a schedule or table in your response.

Response:

Participants' basic demographics (age, gender, race)

Past medical history as it pertains to inclusion/exclusion criteria (co-morbidity status)

Frailty status and parameter scores (Gait speed, weight change, grip strength, activity and endurance)

Short physical performance battery status and parameter scores (Gait speed, chair rise test, balance testing)

Mental status score (VA SLUMS instrument and Cognivue Carity)

Activities of daily living score (ADLs instrument)

Quality of life score (Q-LES-Q-SF instrument)

Physical activity enjoyment score (PACES instrument)

Sleep Quality (PSQI Instrument)

Leisure-time physical activity (Fitbit activity monitor)

Heart rate max score (VO2max test)

Quadriceps strength (MicroFET2 device)

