12.0 Study Timelines

12.1 Describe the anticipated duration needed to enroll all study subjects.

Response: 18 months from the start date of funding (October 1st, 2018)

The post-training assessment will be completed by September 28th, 2021.

12.2 Describe the duration of an individual subject's participation in the study. Include length of study visits, and overall study follow-up time.

Response: Once enrolled in the study the participant will be administer baseline assessment protocols that combined will take approximately 2 hours. The individual will then perform 12 sessions (3 per week – Monday, Wednesday, and Friday) of HIIT exercise. The exercise protocol plus body weight and blood pressure measurements will take no more than 20 minutes. A final assessment will also take approximately 2 hours. Participants in the post-HIIT examination will be required to participate for one additional visit.

12.3 Describe the estimated duration for the investigators to complete this study (i.e. all data is collected and all analyses have been completed).

Response: Two years from the enrollment of the last participant. Post-HIIT assessment will require three months to complete.

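### Three operative figures contradict each other: follow-up payment ($250 or $2500), planned session count (12 or 36), and the intensity measure for the last interval (VO2max or HRmax)

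*Combined protocol and SAP*

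**What the plan says.** **Payment.** Section 8.6 answers a prompt about vulnerable groups and undue influence. It says that the training-phase sum of about $400 "is fair based on the length of the study and that travel to the VAMC during the 3-4-month period is required". For the post-training examination it then lists a Fitbit plus "250 dollars for their participation". Section 26.0 sets out the payments themselves: $100 for the baseline assessments, "300 for completion of endpoint assessments", and for the follow-up a Fitbit plus a check of "2500 for time spent, travel costs, and participation".

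Section 12.2 describes the follow-up burden: "Participants in the post-HIIT examination will be required to participate for one additional visit". Section 11.1 adds: "For a duration of 7-days, leisure-time physical activity will be measured using Fitbit activity monitors".

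**Status.** Section 6.1 says that recruitment has ended and "we will only be completing the 27 subjects with their final visit". It also says: "We will update the protocol and ICF to reflect this information". Section 12.1 plans to finish the post-training assessment by September 28th, 2021.

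**Sessions.** Section 12.2 plans 12 sessions, three per week. Section 11.1 plans three days a week over 12 weeks and refers to the completion of 36 sessions. Section 22.1 also gives 36 sessions over 12 weeks.

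**Last interval.** Section 5.1 sets the fourth and last high-intensity minute at the wattage matching 80% of VO2max, the same as the first three. Section 11.1 gives 80% of VO2max for the first three and 80% of HRmax for the last.

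**The concern.** Each pair describes the same thing and cannot be followed or reported as it stands.

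The payment conflict reaches furthest forward, because the follow-up is the part of the study that the current text still presents as outstanding. Staff who follow 26.0 and staff who follow 8.6 would pay amounts that differ by a factor of ten. The section that deals with undue influence argues only for the training-phase sum and offers no argument for either follow-up amount.

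The other two conflicts concern what the intervention was. The prompt for section 11.1 asks for enough detail that another investigator could replicate the work. A reader cannot tell from the protocol whether the planned programme had 12 or 36 sessions, or which measure set the last interval. In a pilot meant to show that the regimen can be delivered, any report of sessions attended against sessions planned needs a single planned number.

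**Working it through.** **Payment**

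Inputs: $250 (8.6); $2500 (26.0); $100 and $300 (26.0); about $400 (8.6); 27 subjects (6.1).

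- Training phase: 100 + 300 = 400, which matches the figure in 8.6. The two sections agree here, so the conflict is confined to the follow-up amount.
- Ratio: 2500 / 250 = 10.
- Gap per participant: 2500 − 250 = $2,250.
- Against the training-phase payment: 250 / 400 = 0.625 times, or 2500 / 400 = 6.25 times.
- Total if all 27 return: 27 × 250 = $6,750, against 27 × 2500 = $67,500. The gap is 27 × 2,250 = $60,750.

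The protocol does not say how many will return. The total gap therefore runs from $2,250 (one returns) to $60,750 (all 27 return).

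**Session count**

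Inputs: 12 sessions at 3 per week (12.2); 3 per week for 12 weeks, and 36 sessions (11.1); 36 sessions over 12 weeks (22.1).

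- Sections 11.1 and 22.1: 3 × 12 = 36. These agree with each other.
- Section 12.2: 12 / 3 = 4 weeks, which does not agree with a 12-week programme.
- Ratio: 36 / 12 = 3. The one or two optional extra sessions in 11.1 and 22.1 do not bridge the gap.

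**Last interval**

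| | First three hard minutes | Last hard minute |
|---|---|---|
| 5.1 | 80% VO2max, as watts | 80% VO2max, as watts |
| 11.1 | 80% VO2max | 80% HRmax |

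The durations cannot settle this. The steps are 30 seconds, 3 minutes, three pairs of 1 + 1 minutes, 1 minute and 1 minute: 0.5 + 3 + 3 × (1 + 1) + 1 + 1 = 11.5 minutes. That reproduces the stated total under either measure. Nor can the HRmax wording be dismissed because the value was unavailable: section 11.2 lists a maximum heart rate from the VO2max test among the data collected.

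**The case against.** The strongest case against is that these are drafting slips of no statistical consequence. The $2500 may be a misplaced digit. Section 12.2 stands alone on session count, against 11.1, 22.1 and every other mention of a 12-week or 3-month programme. Section 11.1 also adjusts the workload every two weeks and by Borg score, so a nominal percentage does not by itself describe what was delivered. Much of this stands. It limits the importance of the point, but it does not make the passages agree. A slip in a payment amount, a session count or an intensity target is still one that someone may act on or report.

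Two points of timing also stand. If the September 2021 date has passed, the payment item is a correction to the record and no longer a safeguard before visits. The update promised in 6.1 concerns the enrolment number, and the present text may already be that update, so it cannot be assumed to be still open.

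On the payment rationale, 26.0 does state a basis (time, travel and participation). What is absent is any fairness argument in 8.6 for the follow-up sum.

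A reader might infer more than the documents support:

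- **That participants were promised the wrong sum, or that an undue inducement was offered.** The consent form is not in the material reviewed, and nothing shows which amount was approved or paid.
- **That the session count decides who belongs in the follow-up group.** Hypothesis 1.2 defines that group by 12 weeks of training. No section sets a session threshold for completion, and the analysis in 18.1 uses none.
- **That the results would change.** Section 18.2 gives no power calculation, and the paired comparisons in 18.1 use none of the three figures.

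**Conclusion.** The point holds as three unresolved contradictions in the current text, and it should be fixed. The follow-up payment differs tenfold, by $2,250 per participant. The planned session count differs threefold. The last interval is set on two different measures, and the size of that difference in delivered workload cannot be worked out from the protocol.

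The payment total depends on how many of the 27 return, which is assumed. Treating the payment as still open depends on the final visit in 6.1 being the follow-up visit described in 1.1, and on some of those visits still being due. The session count and interval conflicts concern a training phase that 1.1 places about 16 months before the follow-up, so for that group they bear on the record and on reporting. Design, sample size, alpha, power and planned analyses are unaffected.

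**What to change.** 1. Reconcile 8.6 with 26.0 and check both against the approved consent form, before any follow-up visit still to be done. If the visits have taken place, correct the record to show the amount approved and paid. Have 8.6 address that amount.
2. Reconcile 12.2 with 11.1 and 22.1, and use one planned session count wherever attendance or completion is reported.
3. Reconcile 5.1 with 11.1 on the last interval, and report the regimen as it was delivered.

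Which figure is right is for the investigators to establish from their own records.

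The cost is a wording amendment to the sections named. It can go with the protocol and consent-form update mentioned in 6.1 if that is still pending, and otherwise needs a short amendment or a note to the record.
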